11.9.14.2. Clinical Laboratory Tests for Safety

Clinical laboratory tests are summarized in Table 14 and will be performed by a central laboratory, except for urinalysis, according to the relevant schedule of assessments. Additional (unscheduled) local laboratory samples for safety or repeat tests may be collected, if clinically indicated.

All laboratory test results that are abnormal and considered clinically significant must be reported as AEs (Section 11.9.14.3.1). If a clinically significant laboratory AE is supported by a corresponding local lab result, but not by the central lab result, the local lab result will be recorded. All samples will be collected in accordance with acceptable laboratory procedures and graded for toxicity as defined by the National Cancer Institute (NCI)-CTCAE, v5.0.

Available local laboratory test results should be used for treatment management decisions and initial assignment of CTCAE grading. Every effort should be made to discuss any changes to study drug dosing with the Sponsor before implementation, and only if not feasible beforehand, to inform the Sponsor within the same day. Central laboratory results will be used for final assignment of CTCAE grading. In the case of different grades associated with local versus central laboratory results for AEs, the Investigator should determine which laboratory values will be used to document grading of AEs. The local vs central laboratory result with the highest grade should be considered to document grading of AEs.

Hematology	Coagulation	Chemistry	Urinalysis (dipstick) ^a
Hematocrit	Activated partial	Alanine	Hemoglobin
Hemoglobin	thromboplastin time	aminotransferase	Glucose
Platelet count	Prothrombin time	Albumin	Ketone
Red blood cell count	International	Alkaline phosphatase	Protein
White blood cell count with differential	normalized ratio	Aspartate aminotransferase	Specific gravity
		Bicarbonate	
		Calcium	
		Cholesterol	
		Chloride	
		Creatine phosphokinase	
		Creatinine	
		Gamma-glutamyl transferase	
		Glucose	
		Potassium	
		Sodium	
		Magnesium	
		Phosphorus	
		Total bilirubin	
		Conjugated (direct) bilirubin	
		Unconjugated (indirect) bilirubin ^b	
		Total protein	
		Triglycerides	
		Blood urea nitrogen	

Table 14: Clinical Laboratory Tests

^a An additional microscopic examination will be performed if any dipstick analytes are 2+ or higher. A participant should undergo further assessment (eg, a 24-hour urine collection) if the protein analyte is \geq 2+.

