12.4.6. Safety Analyses

Participants from the Safety Set will be included in safety analyses.

AEs will be coded using the MedDRA for purposes of summarization. All AEs occurring on study will be listed in by participant data listings. Treatment-emergent AEs will be tabulated, where treatment emergent is defined as any AE that occurs after administration of the first dose of study drug and through 30 days after the last dose of study drug. Tabulations for all TEAEs, treatment-emergent SAEs, related TEAEs, dose reduction, dose interruptions, and discontinuation of study drug due to AE will be produced. By participant listings will be provided for deaths, SAEs, and AEs leading to discontinuation of study drug.

Change from baseline in clinical laboratory parameters will be summarized across time on study, and the frequency of clinically significant abnormal laboratory values will be tabulated.

Changes in ECG intervals (QT, RR, QTcF, HR, QRS) and vital sign parameters (including systolic and diastolic blood pressure, heart rate, respiration rate, and temperature) will be summarized over time in a similar fashion to laboratory parameters, and any abnormal values will be tabulated. Changes in ECG findings will be presented in data listing format.

Additional safety assessments such as ECGs will be listed by participant.

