4.3. Other Secondary Endpoints

- ORR per RECIST v1.1
- ORR assessed by mRECIST at Week 25
- Duration of response (DOR; time from first PR or CR to disease progression or death) assessed using RECIST v1.1, TVS, and mRECIST
- Incidence of TEAEs, treatment-emergent serious adverse events, related TEAEs, dose reductions, dose interruptions, and discontinuation of study drug due to adverse event
- Changes from baseline in laboratory parameters, electrocardiograms (ECGs), and vital signs

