9.11.3. Clinical Laboratory Tests

The following laboratory parameters will be summarized:

Hematology	Serum Chemistry	Coagulation	Urinalysis (dipstick) ^a
Hematocrit Hemoglobin Platelet count Red blood cell count WBC with differential	Alanine aminotransferase Albumin Alkaline phosphatase Aspartate aminotransferase Bicarbonate Calcium Cholesterol Chloride Creatinine Gamma-glutamyl transferase Glucose Potassium Sodium Magnesium Phosphorus Total bilirubin Conjugated (direct) bilirubin Unconjugated (indirect) bilirubin ^b Total protein Triglycerides Urea (blood urea nitrogen)	Activated partial thromboplastin time Prothrombin time International Normalized Ratio	Hemoglobin Glucose Ketone Protein Specific gravity

^a An additional microscopic examination will be performed if any dipstick analytes are 2+ or higher. A participant should undergo further assessment (eg, a 24-hour urine collection) if the protein in analyte is >=2+

^b Will be calculated by central laboratory.

Descriptive statistics (number of observations, mean, median, standard deviation, minimum, and maximum values) will be presented for clinical laboratory tests. Changes from baseline (including baseline value) by treatment group will be summarized at each scheduled visit. Graphical presentations may also be generated for specific laboratory parameters by visit and treatment group to investigate the trend over time and outliers in the data.

Abnormal laboratory results will be graded with NCI CTCAE version 5.0, if applicable. A shift table, presenting the 2-way frequency tabulation for baseline and the worst post-baseline values according to the NCI CTCAE grade, will be provided by treatment group for hematology and serum chemistry.

A Hy's law summary table and plot will be provided. A plot of alkaline phosphatase vs. total bilirubin will be provided.

A comprehensive listing of all hematology, chemistry (including CPK added in Protocol Amendment 3), coagulation, urinalysis, and pregnancy results will be provided for the SAF. The listing will include the test result, the normal range, change from baseline, and CTCAE grade. Separate listings for hematology and chemistry presenting clinically significant abnormalities or abnormalities of CTCAE grade 3 or 4 will be provided.

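### CPK is the only protocol laboratory analyte left out of the SAP's laboratory summary tables; it is named only for a listing

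*SAP*

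**What the plan says.** Protocol 11.9.14.2, Table 14, lists "Creatine phosphokinase" among the central-laboratory chemistry tests. Protocol 12.4.6 states: "Change from baseline in clinical laboratory parameters will be summarized across time on study". It adds that the frequency of clinically significant abnormal values will be tabulated, and it exempts no analyte. SAP 4.3 makes this an other secondary endpoint: "Changes from baseline in laboratory parameters, electrocardiograms (ECGs), and vital signs".

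SAP 9.11.3 introduces a four-column table with "The following laboratory parameters will be summarized". Its serum chemistry column goes from chloride to creatinine, with no CPK between them. The outputs that follow are:

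- By-visit descriptive statistics: "Changes from baseline (including baseline value) by treatment group will be summarized at each scheduled visit".
- A shift table of baseline against worst post-baseline CTCAE grade, which "will be provided by treatment group for hematology and serum chemistry".
- A comprehensive listing covering "chemistry (including CPK added in Protocol Amendment 3" along with the other panels, which shows each value with its CTCAE grade, its change from baseline and its reference range.
- A narrower output limited to notable values: "Separate listings for hematology and chemistry presenting clinically significant abnormalities or abnormalities of CTCAE grade 3 or 4 will be provided".

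SAP Section 1 says that the SAP is written to Amendment 3, that it prevails over the protocol on statistical analyses, and that any differences will be shown in Section 11. Section 11 reports no major changes and does not mention CPK.

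**The concern.** Because the SAP prevails where the two documents differ, leaving CPK out of its table has effect: a programmer following SAP 9.11.3 would produce no CPK summary. The protocol's general promise would then go unmet for one analyte, with no declared reason.

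The analyte matters. Protocol 5.2 shows CPK increase as by far the most frequent Grade 3 or higher treatment-emergent event among those it lists for the Phase 1/2 TGCT patients. At stake is a planned comparison of CPK by arm over time, and a clear count of CPK grades among those tested. SAP Section 9 treats analyses designed after database lock as post hoc and exploratory, so a CPK table added later would carry that label.

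**Working it through.** **1. Compare the two tables, analyte by analyte** (the SAP's urea entry is taken as the protocol's blood urea nitrogen).

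| Panel | Protocol Table 14 | SAP 9.11.3 | In protocol, not in SAP |
|---|---|---|---|
| Hematology | 5 | 5 | none |
| Coagulation | 3 | 3 | none |
| Chemistry | 22 | 21 | CPK |
| Urinalysis | 5 | 5 | none |
| Total | 35 | 34 | CPK |

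Nothing in the SAP table is absent from Table 14. A PDF reading error is an unlikely explanation: the other 21 chemistry analytes stand in the protocol's order, and the listing sentence adds CPK separately.

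**2. Trace CPK through each SAP output.**

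- *By-visit statistics and change from baseline:* tied to the table, so CPK is not included.
- *Shift table:* unclear. Its scope is serum chemistry, which is the heading of the column that lacks CPK. The listing sentence in the same section counts CPK as chemistry.
- *Comprehensive listing:* included by name.
- *Listing of clinically significant or Grade 3/4 values:* included if chemistry is read as in the CPK sentence.
- *TEAE tables (SAP 9.11.2):* included only where CPK increase is reported as an adverse event. Protocol 11.9.14.3.8.1 requires that for abnormalities the Investigator judges clinically significant, on the basis of related signs or symptoms, further testing or intervention, or a change in study drug. An elevation meeting none of these need not appear.

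**3. Context from Phase 1/2 (protocol 5.2).** CPK increase of Grade 3 or higher: 29 (33.3%). AST increase and hypertension: 4 (4.6%) each. Lipase and amylase increase: 3 (3.4%) each.

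- *Implied denominator:* 33.3% to one decimal requires N between 29/0.3335 = 86.96 and 29/0.3325 = 87.22, so N = 87. Check: 4/87 = 4.6% and 3/87 = 3.4%, as printed.
- *Clopper-Pearson 95% CI for 29/87:* 23.6% to 44.3%.
- *Expected number if that rate held in the vimseltinib arm:* 80 × 29/87 = 26.7.
- *95% prediction interval:* beta-binomial with a Jeffreys prior, posterior Beta(29 + 0.5, 58 + 0.5) = Beta(29.5, 58.5), giving 16 to 39 of 80. A uniform prior gives the same integers.

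The documents do not say how many participants have CPK measured. Under two assumed values, the expected counts are 40 × 29/87 = 13.3 (7 to 21) and 20 × 29/87 = 6.7 (2 to 11).

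These counts are context only. They rest on an adverse-event rate across dose cohorts, not a laboratory-grade rate at the Phase 3 dose, and they do not measure the effect of omitting a summary.

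**The case against.** The strongest defence is that the omission looks deliberate and costs little. The SAP authors noted that CPK was added in Amendment 3 (31 May 2023) and placed it in the listing. Under SAP 8.1, baseline is the last value before first dose, so participants dosed before the test was added may have none. If very few have one, Part 1 change-from-baseline rows by arm would be sparse or empty. Meanwhile CPK events reported as adverse events are still tabulated by arm and maximum grade, and that is the type of data behind the 33.3%. The shift table is defined by panel and may well include CPK.

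Much of this stands. The data are not hidden, the shift table is ambiguous and not clearly lost, and missing baselines are a real possibility that the documents do not let us size.

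It does not close the point, for three reasons. The SAP never gives incomplete data as the reason for listing only, and Section 1 promises that any difference, not just a major one, will appear in Section 11. Adverse-event tables depend on the Investigator's judgement of clinical significance and give no denominator of those tested. Worst post-baseline grade needs no baseline, so missing baselines do not justify having no table at all.

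**Conclusion.** The concern holds. One of 35 protocol laboratory analytes has no planned by-visit or change-from-baseline summary in the SAP, and no table of its grades among those tested is clearly promised. The departure from protocol 12.4.6 is undeclared, and it falls on the analyte with the most frequent Grade 3 or higher event in the prior TGCT data.

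The effect is confined to safety reporting; efficacy, alpha and power are untouched. The omission from the table is certain from the text. How much information is lost depends on how many participants had CPK measured, with and without a baseline, and on how the shift table is read. The documents settle neither. It should be corrected before database lock.

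**What to change.** Add CPK to the serum chemistry column of SAP 9.11.3 and state that the CTCAE shift table includes it. Report the number of participants with CPK measured, in both safety approaches of SAP 9.11 (Part 1 by arm, and all data while on vimseltinib).

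If the sponsor prefers not to summarize change from baseline because CPK was added late, say so in SAP Section 11 and still tabulate worst post-baseline CTCAE grade among those tested.

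The cost is one more analyte in existing table programs; change from baseline and CTCAE grade are already needed for the listing. The drawback is missing baselines for participants dosed before CPK was added. This affects Part 1 by arm and also the pooled vimseltinib data: crossover participants can take a baseline from the End of Part 1 chemistry sample, but the arm first randomized to vimseltinib keeps its pre-first-dose baseline. Showing the number tested makes that limit visible.

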5.2. Risk-benefit Assessment

Patients diagnosed with malignant solid tumors or TGCT have enrolled in Phase 1/2 Study DCC-3014-01-001. As of 09 Nov 2021, approximately 54% of patients experienced adverse events (AEs) of Grade 3 or higher. Treatment-emergent AEs of Grade 3 or higher reported in more than 1 TGCT patient were blood creatine phosphokinase (CPK) increased 29 (33.3%), aspartate aminotransferase (AST) increased 4 (4.6%), hypertension 4 (4.6%), lipase increased 3 (3.4%), and amylase increased 3 (3.4%). Observed elevations in transaminase were not associated with symptoms and were not accompanied by bilirubin elevations and/or other signs of liver damage. Safety laboratory values, cardiac function, and clinical signs and symptoms will be monitored throughout the study. Dosing modification guidelines are included in the protocol for AE monitoring (see Section 9.6). Please refer to the Investigator's Brochure (IB) for currently available clinical safety data.

Effects on embryo-fetal development were studied in rats, and vimseltinib was determined **CC** Participants in this study are advised to avoid pregnancy and are required to use highly effective contraception during the study and for 60 days following the last dose of study treatment for females and 120 days for males. Additional details on the available nonclinical toxicology data and clinical safety data are provided in the IB.

Among efficacy evaluable TGCT patients, objective responses were observed as measured by Response Evaluation Criteria in Solid Tumors (RECIST) v1.1 by independent radiological review (IRR) that were sustainable over time. Updated anti-tumor activity data as of 07 Jun 2021 demonstrated an objective response rate (ORR) of 50% in 32 patients across 3 dose escalation cohorts, and an ORR of 42% (all partial response [PR]) in 19 patients in expansion Cohort A at the recommended Phase 2 dose (RP2D), which is also the selected Phase 3 dose. Objective responses were generally achieved after at least 2 cycles of treatment and responses were durable.

The clinical experience continues to support further study of vimseltinib in the TGCT patient population. The risk to participants appears acceptable, and the benefit-risk balance of vimseltinib treatment in TGCT patients for the Phase 3 study is considered positive.

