1. INTRODUCTION

This statistical analysis plan (SAP) contains definitions of analysis populations and endpoints, and provides a comprehensive description of statistical analyses to be implemented to assess the clinical efficacy, safety and tolerability of vimseltinib in the Phase 3, Randomized, Placebocontrolled, Double-blind Study of Vimseltinib to Assess the Efficacy and Safety in Patients with Tenosynovial Giant Cell Tumor (MOTION) (Protocol DCC-3014-03-001 Amendment 3, dated 31 May 2023).

If there are any differences between the protocol's statistical analysis section and the present document, this SAP will be the primary reference for the study's statistical analyses. Any differences will be highlighted in Section 11.

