7.4. Safety Analysis Set (SAF)

The Safety Set (SAF) consists of participants who have received at least one dose of study treatment. Analysis will be performed according to the treatment regimen actually received.

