9.11. Safety Analysis

All safety analyses will be conducted on the SAF. If there are both local and central assessments in the same nominal visit, then the central assessment will be used for analyses. The safety data will be summarized following two different approaches. The first approach will be limited to data from Part 1 and will focus on comparisons between participants who received vimseltinib versus participants who received placebo during this period. The second approach will combine data from both Part 1 and Part 2 (including extension period) and will focus on the observations and assessments while participants are receiving vimseltinib. Therefore, in this second approach, participants randomized to Placebo in Part 1 who crossed over to vimseltinib in Part 2, will have as their reference day the first dose date of vimseltinib in Part 2, and their data from Part 1 while receiving placebo will be excluded.

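### CPK joined the laboratory panel only with Protocol Amendment 3, yet CPK-increase TEAE rates use the full Safety Set, so any Part 1 visits before the amendment would dilute the Part 1 rate

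*SAP*

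**What the plan says.** SAP 9.11.3 describes the laboratory listing as covering "chemistry (including CPK added in Protocol Amendment 3". SAP Section 1 identifies the governing version as "Protocol DCC-3014-03-001 Amendment 3, dated 31 May 2023". Table 14 of the current protocol (11.9.14.2) has "Creatine phosphokinase" in its chemistry column.

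For the denominator, SAP 9.11 states: "All safety analyses will be conducted on the SAF". SAP 7.4 defines that set: "The Safety Set (SAF) consists of participants who have received at least one dose of study treatment". There are two presentations. One is confined to Part 1 and sets vimseltinib against placebo. In the other, "The second approach will combine data from both Part 1 and Part 2 (including extension period", restricted to time on vimseltinib. Under SAP 9.11.2, TEAEs are numbers and percentages of participants by preferred term, each participant counted at most once per term.

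No section limits CPK-related events to participants or time with scheduled testing, reports how much scheduled CPK exists, or separates visits before and after the amendment. The SAP 9.11.3 table of parameters to be summarized omits CPK. CPK is named only for the listing, which is to show change from baseline.

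Protocol 11.9.14.2 makes a laboratory abnormality an AE when the investigator considers it clinically significant, and it permits unscheduled local samples when clinically indicated.

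**The concern.** An asymptomatic laboratory event can be reported only if the test is done. A participant without scheduled CPK stays in the Safety Set denominator and counts as a non-case unless a test is done for another reason. If the Safety Set mixes participants treated before and after CPK was scheduled, the percentage blends a tested group with a largely untested one, and nothing in the output would show it.

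The term matters. Protocol 5.2 lists "blood creatine phosphokinase (CPK) increased 29 (33.3" per cent) among Grade 3 or higher events in Phase 1/2 TGCT patients; the next most frequent are AST increase and hypertension at 4.6% each. Part 1 is also the only randomized, placebo-controlled safety comparison in the trial. Because CPK is not among the laboratory parameters to be summarized, the AE tables would be the main place where a reader sees a CPK rate.

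There is a related gap. SAP 8.1 defines baseline as the last non-missing value before first study drug. A participant with no CPK before the first dose has no such value, so the change from baseline promised in the listing is undefined for that participant.

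**Working it through.** **1. Reproduce the cited rate.** Protocol 5.2 gives 29 (33.3%), 4 (4.6%) and 3 (3.4%) without a denominator. Of all denominators from 80 to 94, only 87 fits the three together: 29/87 = 33.3%, 4/87 = 4.6%, 3/87 = 3.4%. The figure is consistent.

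**2. What the documents fix and what they leave open.**
- Fixed: CPK entered with Amendment 3 (SAP 9.11.3), dated 31 May 2023 (SAP 1). The denominator is everyone dosed (SAP 7.4, 9.11). The planned vimseltinib arm is about 80 (Protocol 12.1).
- Open: enrolment dates, and the date the amendment took effect at each site. Protocol 13.1.3 requires approval before a change is implemented, so that date follows the amendment date and varies by site. The yield of unscheduled testing is also not given.

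**3. Dilution formula.** Let
- T = true Part 1 rate of Grade 3 or higher CPK increase, taken for illustration as 29/87 = 33.3%, or 26.7 of 80;
- f = share of Part 1 participants with no scheduled CPK (assumed);
- q = share of true cases among those participants found anyway by unscheduled tests (assumed).

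Rate shown on the full Safety Set = T × [(1 − f) + f × q].

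For example, f = 0.50 and q = 0 give 33.3% × 0.50 = 16.7%. With f = 0.50 and q = 0.5 the result is 33.3% × (0.50 + 0.25) = 25.0%.

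| f | q = 0 | q = 0.5 |
|---|---|---|
| 0 | 33.3% (26.7 of 80) | 33.3% (26.7 of 80) |
| 0.25 | 25.0% (20.0) | 29.2% (23.3) |
| 0.50 | 16.7% (13.3) | 25.0% (20.0) |
| 0.75 | 8.3% (6.7) | 20.8% (16.7) |
| 0.90 | 3.3% (2.7) | 18.3% (14.7) |

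If f = 0 or q = 1 there is no dilution. The formula treats each participant as either covered or not. Someone who gained scheduled CPK partway through Part 1 falls between the two.

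**4. Effect on the comparison.** Write k = (1 − f) + f × q. The panel change applies to both arms of a blinded, randomized period, so k should be about the same in each. The displayed difference is then k × T(vimseltinib) − k × T(placebo) = k × the true difference. The absolute difference shrinks by the factor k, while the ratio of the two rates is unchanged.

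**5. Effect of restricting the denominator.** If only participants with scheduled CPK are counted, f drops out and the expected rate is T. This assumes that those participants are representative and were covered for the period analysed.

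**The case against.** The strongest reply is that nothing in the documents shows the problem has any size. No enrolment dates are given, so f could be zero. The SAP's remark that CPK was added suggests that some participants were treated earlier, but it does not prove it. This stands, and it is why the point is conditional.

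The benchmark can also be questioned. The 33.3% comes from a Phase 1/2 study that included dose-escalation cohorts, and no follow-up time is stated. It need not be the 24-week rate at this trial's dose. Under Protocol 11.9.14.3.8.1 an abnormal value becomes an AE only if it meets the clinical-significance criteria, so scheduled testing would not turn every elevation into a TEAE. Both objections stand: 33.3% serves only to illustrate scale.

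Unscheduled local tests would recover some events. This stands too, so the q = 0 column is neither an estimate nor a ceiling on what Part 1 could show.

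Part of the baseline gap resolves itself: SAP 8.1 requires a non-missing pre-dose value and SAP 8.4 uses observed safety data, so no change would be computed where no baseline exists. What remains is that the reader is not told how many participants have one.

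A reader might also infer that CPK increase will appear to rise in Part 2, or in crossover participants, simply because testing began later. The documents do not support that. The SAP plans no Part 2-only TEAE rate. The pooled on-vimseltinib table counts each participant once per term, so it grows with exposure in any case, and a contribution from later testing could not be separated out. Nor do the documents support a claim that testing favours one arm.

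None of this supplies the missing rule. The full-Safety-Set denominator is stated, the change in ascertainment is disclosed, and the two are not connected.

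**Conclusion.** The concern holds conditionally. The plan adds CPK to the panel during the protocol's amendment history and computes CPK-increase TEAE rates on everyone dosed, with no adjustment or disclosure of coverage. If any participants had Part 1 visits before the amendment took effect at their site, the Part 1 rate in each arm and the absolute difference between arms are diluted; the direction is clear.

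The size cannot be derived from the documents. With a true rate of 33.3%, the displayed rate runs from 25.0% to 3.3% for f from 0.25 to 0.90 when nothing is found by other means, and from 29.2% to 18.3% when half is. It stays at 33.3% if f = 0 or q = 1. These figures assume that the Phase 1/2 rate applies and that coverage is all-or-none per participant; the statement about the difference also assumes similar f and q in both arms. It would go too far to say that the reported rate will be far below the truth, or to set a maximum on it.

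**What to change.** Keep the full-Safety-Set figure. Add to SAP 9.11.2 and 9.11.3 one supplementary table of CPK-increase TEAEs and worst CPK CTCAE grade, by arm for Part 1 and for pooled time on vimseltinib. Limit its denominator to participants with at least one protocol-scheduled post-dose CPK in that period. Participants whose only CPK results came from tests done for cause should not enter, because they would enrich the denominator with cases and could overstate the rate.

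Footnote three things:
- the number of participants with scheduled CPK, by arm and period;
- the share of patient time with scheduled CPK, by arm and period, which covers participants who gained testing partway through;
- the number with a CPK value before first vimseltinib, so that the basis for change from baseline is visible.

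The cost is SAP wording and one extra table. The supplementary denominator is smaller, so the estimate is less precise, and the CPK rate may be less favourable. If coverage proves near-complete, the footnote will show that and the two rates will agree closely.
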